7.1.2. Trial Endpoints

Efficacy Endpoints

The efficacy endpoints are defined, as follows:

- Technical Success, defined as a combination of A0 ablations (complete tumor ablation with a surrounding 5 mm margin) and A1 ablations (complete tumor ablation with inadequate margins) based on contrast-enhanced MRI performed up to 7 days following the original ablation procedure.
- Technical Efficacy, defined as a combination of A0 ablations (complete tumor ablation with a surrounding 5 mm margin) and A1 ablations (complete tumor ablation with inadequate margins), based on contrast-enhanced MRI scans at 1 month (+/- 7 days) after the original ablation procedure.
- Local tumor progression (LTP), evaluated at every visit after the ablation of the target tumor(s). LTP describes the appearance of tumor foci at the edge of the ablation zone, after at least one contrast-enhanced follow-up MRI scan has documented adequate ablation and an absence of viable tissue in the target tumor and surrounding ablation margin by using imaging criteria.
- Secondary efficacy rate, defined as the percentage of tumors that have undergone successful repeat ablation following identification of local tumor progression at any time during study follow up.
- Progression-free survival, defined as length of time from the original ablation procedure until any type of disease progression (i.e. local or distant).
- Overall survival measured from the time of the original ablation procedure to the time of death or last follow-up if death has not occurred.

Confidential Page 26 of 61

Safety Endpoint

The safety endpoint is the rate of AEs and SAEs reported at each analysis and cumulatively throughout the entire study period.

Patient Reported Outcomes:

- Pain, as measured by Numeric Pain Rating Scale, before the ablation procedure (measured at Screening Visit), post ablation (within 7 days after ablation]), and at the 1-month follow-up visit.
- Quality of Life, as measured by EORTC QLQ-C30 and liver-specific EORTC QLQ-HCC18, before the ablation procedure (measured at Screening Visit), post ablation (within 7 days after ablation), and at each follow-up visit.

Health Economics:

 Health economics associated with the ablation procedure, including complete procedure time, ablation time, number of ablations, number and types of probes, change in probe position, number of computed tomography (CT) and ultrasound scans performed for probe and margin assessment, and length of hospital stay.

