Microwave ablation (using the Certus Microwave Ablation System only) may be performed for recurrence of target tumor(s) or to achieve complete tumor ablation with adequate margin (A0) of the target tumor(s) if the initial ablation had an insufficient margin, if the treating physician deems appropriate and necessary. While repeat ablations for a recurrence may be conducted at any point during the study duration, repeat ablations to correct an ablative margin may only be performed within the first 30 days of the original ablation (by Visit 3).

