The number and percentage of tumors achieving Technical Success will be summarized and a 95% confidence interval will be estimated. Technical Success will be evaluated based on the margin achieved after the first ablation and prior to any repeat ablations within the first 7 days.

A similar summary will be provided for Technical Efficacy. This endpoint will be based on the scan obtained at Visit 3 and will count as successes patients with A0 or A1 margins in that scan and who did not have an A2 margin since the Visit 2B scan. Additionally, if a patient received a repeat ablation for correcting a margin (to go from A1 to A0) within the first 30 days, this will also count as a success. Patients with repeat ablations to correct an A2 margin from Visit 2B to Visit 3 will not count as success for Technical Efficacy. The number and percentage of tumors with A0 and A1 margins will be presented as a subcategorization within each presentation of Technical Success and Technical Efficacy, as well as a summarization for the number and reasons for repeat ablations through Visit 3.

Local tumor progression rates at 1, 3, 6, 9, 12, 18, 24, 30, and 36 months will be estimated using the Kaplan-Meier method and 95% confidence intervals will be provided. Any repeat ablation required after Visit 3 (Month 1) will be identified as an instance of local tumor progression. A similar summary will be provided for the 36-month overall and progression-free survival rates.

Confidential Page 41 of 61

The number and percentage of patients experiencing AEs will be summarized at the preferred term level using the Society of Interventional Radiology (SIR) clinical practice guidelines for event categorization. A similar summary will also be provided for device-related AEs, procedure-related AEs, all SAEs, device-related SAEs, and procedure-related SAEs. Adverse event rates will also be estimated using cumulative patient years of exposure as the denominator as well as total number of patient ablations.

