A subject archieving technical efficacy is defined as a patient with all tumors reaching A0 or A1 at Visit 3. The number and percentage of subjects archieving Technical Efficacy will be summaried as well. Percentage will be calculated relative to the total number of subjects in relavent analysis population (FAS or PPS). A 95% confidence interval will be estimated using wald method. But the subjects who have any A2 margin since the visit 2B scan would not be counted as technical efficacy regardless if the tumor was corrected with repeat ablation.

Local tumor progression (LTP) (the 2nd interim, final)

LTP is evaluated after the ablation of the target tumor(s). LTP describes the appearance of tumor foci at the edge of the ablation zone, after at least one contrast-enhanced follow-up

MRI scan has documented adequate ablation, and an absence of viable tissue in the target tumor and surrounding ablation margin, by using imaging criteria.

Tumor-level analysis method is same as that of Technical Success endpoint. The number and percentage of tumors with LTP will be summarized and a 95% confidence interval will be estimated using Wald method.

A subject with LTP is defined as a patient with any target tumor LTP. The number and percentage of subjects with LTP. Percentage will be calculated relative to the total number of subjects in relevant analysis population (FAS or PPS).

Subgroup analysis is defined in SAP section 8.11. Two subgroup columns (subjects/tumors with only initial ablation and subjects/tumors with repeat ablation) and 1 total column will be used as analysis columns in LTP tables.

Tumor type (primary HCC and recurrent HCC and other) will be another subgroup variable for LTP (analyzed for patient level and tumor level).

LTP start date is the date of initial ablation of a subject. The event date of LTP is collected in "Ablation Zone Assessment" CRF page as following table:

		Event/Censoring	
	Situation	Date	Outcome
No post-base	eline or no baseline Ablation Zone A	ssessment	
	No post-baseline local tumor	Date of initial	
A1	evaluation	ablation	Censored
	No baseline local tumor	Date of initial	
A2	evaluation	ablation	Censored
With baselin	e and post-baseline tumor assessm	ents	
	Local Tumor Progression and zero or one missed tumor assessment prior to confirmed		
B1	LTP	Date of first LTP date	Event

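### Protocol 8.1 scores receipt of an A1-to-A0 repeat ablation as Technical Efficacy success whatever its result; the SAP subject-level rule does not, and the two are not reconciled

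*Protocol*

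**What the plan says.** Protocol 7.1.2 and 7.1.6 define Technical Efficacy as A0 plus A1 ablations, "based on contrast-enhanced MRI scans at 1 month (+/- 7 days) after the original ablation procedure". Protocol 8.1, repeated in the Synopsis under Statistical Methods, turns this into three scoring sentences:

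1. The Visit 3 scan decides. Successes are "patients with A0 or A1 margins in that scan and who did not have an A2 margin since the Visit 2B scan".
2. In addition, for a patient who had a repeat ablation to correct "a margin (to go from A1 to A0) within the first 30 days, this will also count as a success".
3. "Patients with repeat ablations to correct an A2 margin from Visit 2B to Visit 3 will not count as success for Technical Efficacy".

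SAP 8.4.1 scores subjects differently: "A subject archieving technical efficacy is defined as a patient with all tumors reaching A0 or A1 at Visit 3". Subjects with any A2 since the Visit 2B scan "would not be counted as technical efficacy regardless if the tumor was corrected with repeat ablation". The subject-level denominator is everyone in the FAS or PPS. The SAP gives no credit for having had a repeat ablation.

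At tumor level, SAP 8.4.1 only refers back to the method for the primary endpoint. It does not say how a re-ablated tumor, or a tumor with an earlier A2, is scored.

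**The concern.** Sentence 2 is triggered by receiving a procedure, not by what the procedure achieved. An endpoint meant to record whether the tumor was completely ablated at one month would, for these patients, record that a second ablation was done.

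Three features of the design give this some weight. The study has no hypothesis and no acceptance criterion (Protocol 8.2.2, 8.4), so the descriptive rates are themselves the evidence, in a study intended to support registration in China (Protocol 4.3). The repeat is at the treating physician's discretion (Protocol 7.2.2). The scans are read by the site investigators (Protocol 7.1.6) with no central reviewer (Protocol 7.1.4).

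The sentence is also written per patient, although up to three tumors may be treated and the protocol reports tumor percentages. One tumor's repeat ablation could therefore carry a patient whose other tumor failed.

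**Working it through.** **Sample size.** Protocol 8.2.1 wants 100 patients with data to one year and allows 20% dropout: 100/(1 - 0.20) = 125. Adding 3 × 4 = 12 run-in patients gives 137. Both figures reproduce, and neither depends on the scoring rule.

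**Which patients sentence 2 can add.** Take a single tumor that is A1 at Visit 2B and re-ablated to reach A0, and run through the possible later results. An interim A2 means an A2 on a scan between Visits 2B and 3, with no repeat ablation to correct it.

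| Interim A2? | Visit 3 | Sentence 1 | With sentence 2 | SAP subject rule |
|---|---|---|---|---|
| No | A0 or A1 | success | success | success |
| No | A2 | not | **success** | not |
| No | missing | not | **success** | not |
| Yes | A0 or A1 | not | **success** | not |
| Yes | A2 or missing | not | **success** | not |

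In the first row the clause changes nothing. In every row where it changes the answer, there is an A2 since Visit 2B or no Visit 3 result.

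**Two tumors.** Tumor 1 is A1 and is re-ablated to A0. Tumor 2 is A2 at Visit 2B. Both are A0 or A1 at Visit 3. I read 'since the Visit 2B scan' as including that scan, which sentence 3 supports.

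- Tumor 2 not re-ablated: sentence 1 and the SAP say not a success; sentence 2 says success.
- Tumor 2 re-ablated for its A2: sentence 2 says success and sentence 3 says not. The protocol contradicts itself.

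**Missing Visit 3 scan.** Protocol 8.6 restricts analysis to observed data and rules out imputation. SAP 8.4.1 divides by all FAS or PPS subjects, so an unscanned subject is a non-success. Sentence 2 alone makes that patient a success.

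**Size.** One patient moves the subject-level rate by 1/125 = 0.8 points, or 1/100 = 1.0 point if 100 are analyzed. The documents do not say how many would be affected. Assume 10-20% of 125 are re-ablated for A1 and 10% of those are A2 or unscanned at Visit 3:

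- Low: 125 × 0.10 × 0.10 = 1.25 patients; 1.25/125 = 1.0 point.
- High: 125 × 0.20 × 0.10 = 2.5 patients; 2.5/125 = 2.0 points.

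To show scale, use the 90.95% one-month rate from the 221-patient retrospective series in Protocol 4.1.1: 125 × 0.9095 = 113.7, so 114 successes. With the SAP's Wald interval, p ± 1.96 × √(p(1-p)/125):

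| Patients added | Rate | 95% CI |
|---|---|---|
| 0 | 114/125 = 91.2% | 86.2-96.2 |
| 1 | 115/125 = 92.0% | 87.2-96.8 |
| 2 | 116/125 = 92.8% | 88.3-97.3 |
| 3 | 117/125 = 93.6% | 89.3-97.9 |

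**The case against.** The best defence is that sentences 2 and 3 form a pair: a repeat to correct A1 does not disqualify, and a repeat to correct A2 does. The rule opens by resting on the Visit 3 scan, and this reading fits the endpoint definitions. It may well be what was meant. But it makes sentence 2 redundant, because sentence 1 already counts those patients, and the word 'also' together with the absence of any outcome condition points the other way. A scoring rule should not need that inference.

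The second defence is that the SAP settles the matter. Protocol 8.1 leaves the detail to the SAP, and Protocol 8.7 allows changes to be made there. At subject level this largely stands: the SAP rule is sound. What remains is that the SAP does not identify its rule as a departure from the protocol. Its tumor-level text is silent on re-ablated tumors, so the protocol sentence is the only text that addresses A1 repeats.

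A reader might also draw three stronger conclusions that the documents do not support:

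- *That the reported rate will be inflated.* Under the SAP subject-level rule it is not; that holds only if the protocol clause is applied.
- *That re-ablated patients cannot fail.* Sentence 3 fails every patient re-ablated to correct an A2.
- *That the planned repeat-ablation subgroup would be near 100% by definition.* SAP 8.9 and the closing sentence on subgroups in Protocol 8.1 put all repeats in the first 30 days into that group, including those for A2. Success by definition applies only to A1-to-A0 repeats.

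**Conclusion.** The point holds as an inconsistency that should be corrected, not as a demonstrated bias. Read literally, the Protocol 8.1 and Synopsis clause can only convert patients with an A2 since Visit 2B, or with no Visit 3 result, into successes. It conflicts with the MRI-based definition, the observed-data rule and the SAP subject-level rule, and with the sentence that follows it when another tumor is re-ablated for an A2.

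The logical part rests on the text alone. The +1 to +2 points rests on the two assumed percentages and could be zero if no A1-to-A0 repeat ends in A2 or without a scan. The effect is on a descriptive estimate; no test, power or sample size depends on it. Protocol 8.1 names only Technical Success for the first analysis, but SAP 8.6 adds Technical Efficacy, so the scoring rule is needed from that analysis on.

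**What to change.** In Protocol 8.1 and the Synopsis, replace the clause with:

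> *A repeat ablation within the first 30 days to correct an A1 margin does not by itself make a tumor or patient a failure. A tumor is a success only if it is A0 or A1 on the Visit 3 scan with no A2 since the Visit 2B scan; a patient is a success only if every target tumor meets this.*

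In SAP 8.4.1, state that this rule applies at both tumor and subject level and supersedes the protocol clause. Protocol 8.7 allows the change to be recorded in the SAP.

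The cost is a short wording change in each document. Subject-level scoring under the SAP does not change. The reported rate may be slightly less favourable than under the protocol clause, and the tumor-level rate may also fall if re-ablated A2 tumors would otherwise have been counted as successes. The change concerns endpoint scoring only and does not affect when or whether a repeat ablation is done.

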The largest clinical experience using MW ablation to treat HCC comes from China, in part due to early adoption of MW ablation systems available only in Asia. That multicenter study of 1007 patients with primary liver cancer showed a technical success of 97.1% (1276/1363) and a local tumor progression rate of 5.9% (78/1363) with a mean follow-up time of 17.3 months (range, 3-68.9 months). The 1-, 3- and 5-year overall survival rates were 91.2%, 72.5% and 59.8%, respectively.⁵

A retrospective study of MW ablation as a first-line treatment for HCC evaluated the long-term outcomes and prognostic factors of 221 consecutive patients receiving MW ablation in Renji Hospital (Shanghai) between October 11, 2010 and December 31, 2013 were enrolled. Technique effectiveness was evaluated 1-month post-ablation. Initial complete ablation was found in 201 (90.95%) patients, secondary technique effectiveness in 8 (3.62%) patients, and the remaining 12 (5.43%) patients suffered from incomplete ablation after 2 sessions of MW ablation. No patients died within 30 days post ablation. Major complications occurred in 8 (3.8%) patients. It was concluded that MW ablation provides high technique effectiveness rate and is well tolerated in patients with HCC as a first-line treatment.

Confidential Page 21 of 61

Literature Review

Pre-clinical and clinical data has shown that MW ablation is safe and effective in liver tumors with low complication rates, high rates of technical success, lower rates of local tumor progression and promising disease-free and overall survival rates than have historically been reported for radiofrequency (RF).⁷

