8.2. Calculation of Sample Size

8.2.1. Total Sample Size

The total sample size will be 137 patients. This includes 3 patients at each site who will be part of the run-in phase. There are no stated hypotheses in this study from which a power calculation and sample size determination will be performed; rather, a minimum of 100 patients providing data to at least 1 year is determined to be sufficient to provide an evaluation of safety and effectiveness of the NeuWave Microwave Ablation System. In anticipation of up to 20% dropout, a total of 125 patients will be enrolled after completion of the run-in phase for a total of 137 patients.

8.2.2. Minimum and Maximum Number of Patients in Each Clinical Trial Institution and Reasons for Determination

A total of 137 patients will be enrolled across the 4 study sites. There is no limitation on the number of patients each participating site may enroll. Significance Level and Power of Clinical Trial. No significance level is specified as no hypotheses are being tested in this trial, and therefore no determination of power is made.

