The visit in the outputs should be derived based on the above visit schedule.

If a visit is performed "out of window" (i.e.between two visit windows), the visit should be analyzed as part of the the visit closest in terms of time or number of days as outlined by visit schedule, above. More details can be found in Table 1 of the protocol.

In case any retest performed within one visit, the visit in the outputs will be derived based on the above time windows. The visit with worst result will be used as the planned visit.

5 Levels of Significance

Given that no hypotheses are formally being tested in this study, no levels of significance are specified. Estimation of specified study endpoints will be performed using two-sided 95% confidence intervals (CI).

6 Analysis Sets

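### Protocol 8.1 counts any re-ablation after Visit 3 as local tumour progression, even for residual tumour that the endpoint definition excludes, and the SAP does not settle such cases

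*Protocol*

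**What the plan says.** **Definition.** Protocol 7.1.2, also in the Synopsis and 7.1.6, places LTP at the edge of the ablation zone and admits it only "after at least one contrast-enhanced follow-up MRI scan has documented adequate ablation and an absence of viable tissue". SAP 8.4.1 repeats this.

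**Counting rule.** Protocol 8.1, also in the Synopsis under Statistical Methods, adds: "Any repeat ablation required after Visit 3 (Month 1) will be identified as an instance of local tumor progression". It sets no condition about an earlier scan.

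**Reasons for re-ablation.** Protocol 7.2.2 names recurrence, at any time, and correction of an insufficient margin. On the latter it says: "repeat ablations to correct an ablative margin may only be performed within the first 30 days of the original ablation (by Visit 3". Protocol 8.1 counts a correction from A1 to A0 within the first 30 days as a Technical Efficacy success. Visit 3 is at 1 month, plus or minus 7 days.

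**SAP.** Section 8.4.1 takes the LTP date from the Ablation Zone Assessment CRF page and does not mention the re-ablation rule. It says: "LTP start date is the date of initial ablation of a subject". The patient-level denominator is every subject in the FAS or PPS. Table 3 (censoring rules) has no row for a tumour that no scan ever showed to be completely ablated. Row C censors cases without progression at the last assessment free of LTP.

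**The concern.** Residual tumour after an incomplete ablation (grade A2) and regrowth after a complete one are different outcomes. The definition keeps them apart; the rule in Protocol 8.1 does not. A tumour graded A2 at Visit 2B and again at Visit 3 cannot have LTP by the definition, yet it becomes an LTP event under the rule if it is re-ablated later. This sequence is foreseeable, because Technical Efficacy is read from the Visit 3 scan and any treatment prompted by that scan comes after Visit 3.

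The SAP neither repeats the rule nor explains its absence, although Protocol 8.7 asks for changes to the planned analyses to be specified. Two analysts, one working from each document, could report different LTP rates from the same patients. Secondary efficacy is affected too, since SAP 8.4.1 calculates it among those with LTP who were re-ablated with the device.

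Protocol 8.4 sets no acceptance criterion and judges results against other available therapies. An LTP rate of unclear composition is hard to use in that comparison. LTP is first reported at the 12-month analysis.

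**Working it through.** **Where rule and definition part**

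- *True recurrence after documented complete ablation, re-ablated after Visit 3:* LTP under both. No conflict.
- *A2 at every scan through Visit 3, re-ablated later:* LTP under Protocol 8.1, not LTP under the definition. On the SAP's default reading the case is censored without an event. This last step is inferred from row C and the lack of a specific row. The codes A1 and A2 in Table 3 label missing assessments, not margin grades, and play no part here.
- *Margin correction after an early Visit 3:* Visit 3 can fall between about day 23 (30 − 7) and day 37 (30 + 7). If it falls on day 23 and an A1 margin is corrected on day 27, the procedure is within 30 days and so a Technical Efficacy success. It is also after Visit 3 and so an LTP event. The two limits quoted from Protocol 7.2.2 are one limit only if Visit 3 falls on day 30.

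**Figures in the plan**

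The plan states no expected LTP rate. Its sample size reproduces, 100/(1 − 0.20) = 125 and 125 + 4 × 3 = 137, but does not bear on this point. The background figures come from Protocol 4.1.1 and 4.2:

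- Never complete: "the remaining 12 (5.43%) patients suffered from incomplete ablation after 2 sessions of MW ablation"; 12/221 = 5.43%, as printed.
- LTP: printed as 5.9% (78/1363), but 78/1363 = 5.7%. Dividing instead by 97.1% of 1363, about 1323, gives 5.9%. The printed rate may therefore refer to completely ablated lesions, but that is an inference.
- Range for incomplete ablation: 100 − 97.1 = 2.9% (large Chinese series) to 9/107 = 8.4% (retrospective series with the study device).

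**Formulas**

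Let q be the share never complete, p the LTP rate among completely ablated cases, and f the share of never-complete cases re-ablated after Visit 3. Assume p = 5.9%. The documents do not give f, so it runs from 0 to 1.

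- Definition, at-risk cases only: p
- Default SAP reading, full denominator: (1 − q)p
- Protocol 8.1 rule: (1 − q)p + fq
- Gap between protocol rule and SAP reading: fq, whatever p is

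For q = 12/221 = 0.0543:

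- Definition: 5.9%
- SAP reading: 0.9457 × 0.059 = 0.0558, or 5.6%
- Protocol rule: 5.6% at f = 0; 0.0558 + 0.5 × 0.0543 = 8.3% at f = 0.5; 0.0558 + 0.0543 = 11.0% at f = 1

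| q | Of 125 patients | SAP reading | Rule, f = 0.5 | Rule, f = 1 | Gap at f = 1 |
|---|---|---|---|---|---|
| 2.9% | 3.6 | 5.7% | 7.2% | 8.6% | 2.9 points |
| 5.43% | 6.8 | 5.6% | 8.3% | 11.0% | 5.4 points |
| 8.4% | 10.5 | 5.4% | 9.6% | 13.8% | 8.4 points |

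For scale, the Wald 95% half-width with 125 patients is 1.96 × √(0.056 × 0.944/125) = 4.0 points at 5.6%, and 1.96 × √(0.110 × 0.890/125) = 5.5 points at 11.0%.

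**Kaplan-Meier check**

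A simulation assumed a constant LTP hazard giving 5.9% at 17.3 months, the protocol's visits, 20% dropout by month 36, and late re-ablation at month 3. With q = 5.43% and f = 1, the SAP reading and the protocol rule gave 3.9% and 9.4% at 12 months, and 11.3% and 16.7% at 36 months. The definition gave 4.1% and 11.9%.

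**The case against.** The strongest reply is that the protocol largely closes the gap itself. Section 7.2.2 gives recurrence as the only reason for a late re-ablation, and for recurrence the rule and the definition agree. This stands, and it confines the conflict to the two situations above. It does not remove it: the rule says any, and nothing says how a late re-ablation of residual tumour is to be classified.

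A reader might infer that the SAP deliberately counts never-complete tumours as LTP-free. No SAP sentence says so; it follows only by default from row C. The CRF page and its instructions are not among the documents, so how investigators would record such a case is unknown.

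A reader might also infer that the LTP rate will double. That needs f = 1, a further session for every residual tumour. The 12 patients behind the 5.43% had already had two sessions. The illustration also joins a patient-level share to a lesion-level rate, and using 5.9% for completely ablated cases is an assumption.

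Nor is the rate made uninterpretable. The SAP reports A0, A1 and A2 counts at Visit 2B, fails subjects with any A2 for Technical Efficacy, and summarises repeat ablations through Visit 3. All analyses are descriptive: "Given that no hypotheses are formally being tested in this study, no levels of significance are specified". No pass or fail decision turns on this. Starting the clock at the initial ablation is also defensible, since the first scan follows within 7 days.

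The early-Visit-3 case is an edge case. Read by its Visit 3 limit, Section 7.2.2 would call that correction too late; read by its 30-day limit, it would not. That is why the two limits need reconciling.

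**Conclusion.** The concern holds in a limited form. The Protocol 8.1 rule lacks a condition that the LTP definition requires. The SAP does not carry the rule over, and neither document says how a tumour never documented complete enters the LTP analysis. The conflict is confined to residual tumour re-ablated after Visit 3 and to margin corrections between an early Visit 3 and day 30.

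Under the stated assumptions (q = 5.43%, p = 5.9%), the protocol rule exceeds the default SAP reading by 0 to 5.4 points as f goes from 0 to 1. Over q from 2.9% to 8.4%, the gap is 0 to 8.4 points. It matches or exceeds the interval half-width only if most residual tumours are re-ablated late. The definition and the default SAP reading differ by only 0.3 points (5.9% against 5.6%), so the protocol rule drives the size. The documents do not show that the gap will be large, only that it is left open.

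**What to change.** Use one rule in both documents, before the 12-month analysis:

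- Replace the sentence in Protocol 8.1 and the Synopsis. Count a re-ablation as LTP only if new foci at the edge of the ablation zone were recorded after a scan documenting complete ablation.
- State whether grade A1 counts as adequate ablation for this purpose. The definition leaves this open, since A1 is complete ablation with inadequate margins.
- In SAP 8.4.1, limit the LTP risk set and denominator to tumours documented complete. The clock may stay at the initial ablation.
- Add a Table 3 row for never-complete tumours and report them separately as residual tumour.
- Keep the present Protocol 8.1 rule as a sensitivity analysis.
- Reconcile the 30-day and Visit 3 limits in Protocol 7.2.2 and 8.1. Which limit applies is for the sponsor and investigators to settle.

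The cost is a protocol clarification, a short SAP change and one table row. Ablation grades and LTP assessments are already collected, so no new data should be needed. The CRF instructions should be checked for consistency with the new rule.
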